4.6. Study Treatment Exposure and Compliance Variables

Study treatment exposure variables for infusions administered in Part A are listed below with associated definitions:

- The total number of Part A study treatment infusions by patient.
- Patient duration of Part A observation treatment period in weeks defined as: (last visit date during the Part A observation period - first study treatment administration date in Part A)/7.

Study treatment exposure variables for infusions administered in Part B are listed below with associated definitions:

- Patient duration of Part B study treatment exposure in weeks defined as: (last Part B study treatment administration date +28 – first Part B study treatment administration date)/7. Unplanned intermittent discontinuations in study treatment will be addressed on a case-by-case basis, since this is expected to be a rare occurrence. Values will be rounded to one decimal place.
- The total number of Part B study treatment infusions by patient.
- The following categories will be used for treatment exposure at 4 week intervals: ≥ 1 day and < 4 weeks, ≥ 4 weeks and < 8 weeks, ≥ 8 weeks and < 12 weeks, ≥ 12 weeks and < 16 weeks, ≥ 16 weeks and < 20 weeks, ≥ 20 weeks and < 24 weeks, ≥ 24 weeks.

Study treatment exposure variables for infusions administered in Part C are listed below with associated definitions:

- Patient duration of Part C study treatment exposure in weeks defined as: (last Part C study treatment administration date +28 – first Part C study treatment administration date)/7. Unplanned intermittent discontinuations in study treatment will be addressed on a case-by-case basis, since this is expected to be a rare occurrence. Values will be rounded to one decimal place.
- The total number of Part C study treatment infusions by patient.
- The following categories will be used for treatment exposure at 4 week intervals: ≥ 1 day and < 4 weeks, ≥ 4 weeks and < 8 weeks, ≥ 8 weeks and < 12 weeks, ≥ 12 weeks and < 16 weeks, ≥ 16 weeks and < 20 weeks, ≥ 20 weeks and < 24 weeks, ≥ 24 weeks and < 28 weeks, ≥ 28 weeks and < 32 weeks, ≥ 32 weeks and < 36 weeks, ≥ 36 weeks and < 40 weeks, ≥ 40 weeks and < 44 weeks, ≥ 44 weeks and < 48 weeks, ≥ 48 weeks

Study treatment exposure variables on the integrated data pool (Section 2.4) are listed below with associated definitions:

- Cumulative patient duration of study treatment exposure in weeks defined as: Part C treatment exposure for Part A patients, and Part B treatment exposure plus Part C treatment exposure for Part B patients.
- Cumulative total number of study treatment infusions by patient defined as: total number of Part C infusions for Part A patients, and total number of Part B infusions plus total number of Part C infusions for Part B patients.
- The following categories will be used for cumulative patient treatment exposure at 4 week intervals: ≥ 1 day and < 4 weeks, ≥ 4 weeks and < 8 weeks, ≥ 8 weeks and < 12 weeks, ≥ 12 weeks and < 16 weeks, ≥ 16 weeks and < 20 weeks, ≥ 20 weeks and < 24 weeks, ≥ 24 weeks and < 28 weeks, ≥ 28 weeks and < 32 weeks, ≥ 32 weeks and < 36 weeks, ≥ 36 weeks and < 40 weeks, ≥ 40 weeks and < 44 weeks, ≥ 44 weeks and < 48 weeks, ≥ 48 weeks and < 52 weeks, ≥ 52 weeks and < 56 weeks, ≥ 56 weeks and < 60 weeks, ≥ 60 weeks and < 64 weeks, ≥ 64 weeks and < 68 weeks, ≥ 68 weeks and < 72 weeks, ≥ 72 weeks, etc.

With respect to patient treatment administration compliance, the study treatment is administered during the investigative site visits and therefore study compliance will be assessed by infusion frequency for Part B treatment period, and Part C treatment period, specifically:

- The mean infusion/injection frequency for study treatment will be defined for each patient as the average number of days between 2 consecutive infusions: (last study treatment administration date – first study treatment administration date) / (number of infusions - 1), for patients receiving at least 2 infusions.

All important and minor protocol deviations potentially impacting efficacy analyses, drug-dispensing irregularities, as well as other deviations, will be collected and reviewed on an ongoing basis throughout the study as described in the Protocol Deviation Plan (PDP). Both monitoring collected and programmatically derived deviations are listed and defined in the PDP.

4.7. Efficacy Variable

Efficacy will be assessed through the following lipid parameters: calculated LDL-C (using the Friedewald formula), total cholesterol (TC), non-HDL-C (calculated by subtracting HDL-C from TC), Apo B, and Lp(a). All lipid parameters will be collected over the course of the study and sent to a central laboratory for evaluation, including scheduled and unscheduled blood draws.

All lipid values obtained during the study (scheduled or unscheduled), regardless of fasting status (fasting or not fasting), can be used to provide a value for the primary and secondary efficacy endpoints, with the following exceptions:

1. On the day of apheresis, any lipid values collected after apheresis for the respective visit will be excluded from the efficacy analyses.

All efficacy measurements will be assigned to efficacy analysis windows defined in [Appendix 10.2](#) of this SAP, with the intent to provide an assessment for week 1 to week 24 timepoints for Part B. For all time points post-baseline, the value used for the analyses at a given

time point (e.g. at week 24) is the value obtained within the corresponding efficacy analysis window. The baseline value is defined as the last available measurement prior to the date of the first study treatment administration regardless of the study treatment period.

4.7.1. Primary Efficacy Variable (s)

The primary efficacy endpoint for Part B is:

- The percent change in calculated LDL-C from baseline to week 24 (intent-to-treat [ITT] estimand) in Part B. The primary endpoint is defined as: $100 \times (\text{calculated LDL C value at week 24} - \text{calculated LDL-C value at baseline}) / \text{calculated LDL-C value at baseline}$.

The baseline LDL-C value is defined as the last calculated LDL-C value obtained before the first dose of study treatment in Part B. The calculated LDL-C at week 24 will be the LDL-C value obtained within the week 24 analysis window.

The intent-to-treat estimand used for the primary efficacy analysis is the treatment policy strategy, specifically the occurrence of the intercurrent events is irrelevant; the value for the primary efficacy endpoint is used regardless of whether or not the intercurrent events occur. The intent-to-treat estimand for the primary efficacy analysis is defined as:

- A. The patient population is defined as the Intent-to-treat population (Section 3.1.1).
- B. The primary efficacy endpoint is defined above.
- C. The intercurrent events of interest are the administration of study treatment and the administration of subsequent therapies. The interruption of study treatment and the change in subsequent therapies are ignored, and the value for the primary efficacy endpoint is used regardless of adherence to study treatment and subsequent therapies.
- D. The population-level summary for the primary efficacy endpoint is evinacumab mean value, SE and 95% confidence interval.

4.7.2. Secondary Efficacy Variable(s)

The secondary continuous efficacy endpoints in Part B are provided below, applying the ITT estimand described for primary efficacy endpoint (Section 4.7.1 definitions A, C and D).

- The percent change in Apo B from baseline to week 24 (ITT estimand)
- The percent change in non-HDL-C from baseline to week 24 (ITT estimand)
- The percent change in TC from baseline to week 24 (ITT estimand)
- The percent change in calculated LDL-C from baseline to week 24 in patients who have negative/negative and null/null mutations (ITT estimand)
- The percent change in Lp(a) from baseline to week 24 (ITT estimand)
- The absolute change in LDL-C at week 24 (ITT estimand)

The secondary binary efficacy endpoint in Part B is provided below, applying the ITT estimand described for primary efficacy endpoint (Section 4.7.1 definitions A and C). The definition for the population-level summary (definition D) is evinacumab proportion and 95% confidence interval.

- The proportion of patients with $\geq 50\%$ reduction in calculated LDL-C at week 24 (ITT estimand)

4.8. Safety Variables

Patient safety will be assessed through the collection of reported adverse events (AEs), clinical laboratory data, vital signs, Tanner stages and ECG. Unless otherwise noted, the baseline value is defined as the last available value before the first dose of study treatment, regardless of the study treatment period.

4.8.1. Adverse Events Variables

The period of safety observation starts from the time when the patient gives informed consent and continues into the following periods:

- The PRE-TREATMENT period is defined from the day the ICF is signed to the day before the first dose of study treatment administration.
- The treatment-emergent adverse event (TEAE) period (Part A or Part B) is defined from the day of the first dose of study treatment administration to the day of the last dose of study treatment administration in Part A or Part B respectively + 168 days (24 weeks). For patients entering Part C, the TEAE period is truncated at the day before the first study treatment administration in Part C.
- The Part C TEAE period is defined from the day of the first study treatment administration in Part C to the day of the last study treatment administration in Part C + 168 days (24 weeks).
- The pooled TEAE period is defined below:
 - Part A Patients: defined as the Part C TEAE period.
 - Part B Patients: defined from the day of the first study treatment administration in Part B to the day of the last study treatment administration in Part C + 168 days (24 weeks) or to the last study treatment administration in Part B + 168 days (24 weeks) for patients not entering into Part C.
- The POST-TREATMENT period is defined from the day after the end of the respective TEAE periods to the last study visit.

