14. At weeks 8 and 16 of the follow-up period all patients will be contacted by phone to query LMT compliance, to inquire about AEs or changes to concomitant medications, confirm required contraception use, and remind patients of pregnancy reporting. Sexually active females of childbearing potential will report the results of their home pregnancy test. For patients who decide to enter a compassionate use or early access program, the EOT visit will be their last visit and they will forgo the 24-week follow-up period.
15. Overlapping assessments completed at the EOT visit of Part A or Part B do not need to be duplicated during visit 1 of Part C. Part C visit 1 should occur on the same day as Part A visit 11 or Part B visit 11. All necessary assessments are listed in the applicable SOE (Part A or Part B) column for visit 11.
16. Patient can only receive the dose once all assessments from Part A or Part B Visit 11 are completed.
17. For patients who decide to enter a CUP or EAP, the EOT visit will be their last visit and they will forgo the 24-week follow-up period.

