2.3. Study Plan

Part A and Part B are the two main study parts. Part C is an extension for patients from both Part A and Part B.

[figure not shown]
Part A consists of up to 4 periods: run-in; screening; single-dose open-label treatment and 16-week observation, and a 8-week follow-up period (for patients who do not enter Part C). Upon completion of Part A, patients will have the opportunity to continue into Part C (See Figure 1).

Figure 1: Study Flow Diagram Part A

Part B consists of up to 4 periods: run-in; screening; 24-week open-label treatment period; 20-week follow-up (for patients who do not enter Part C) (See Figure 2)

[figure not shown]
Figure 2: Study Flow Diagram Part B

Part C consists of 2 periods: a 48-week treatment period and a 20-week follow-up period (See Figure 3). Patients who participate in Part C should enter directly from Part A or Part B. The first visit (visit 1) in Part C can occur on the same day as the EOT visit in Part A (visit 11)/Part B (visit 11). Overlapping assessments completed at the EOT visit do not need to be duplicated during visit 1 in Part C.

All patients from Part A who enter Part C will initially receive open-label evinacumab 15 mg/kg IV Q4W. The final dose in Part C will be the same as the dose in Part B; therefore, the dose in Part C for patients entering from Part A may need to be adjusted to align with the dose in Part B.

Figure 3: Study Flow Diagram – Extension

The Study event table is presented in Appendix 10.7 .

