5.8. Analysis of Safety Data

In general, for main study part (Part A or Part B), the summary of safety results for patients in the safety analysis set will be presented by each study part. No formal inferential testing will be performed. Summaries will be descriptive in nature.

For Part C, the summary of safety results for patients in the Part C safety analysis set will be presented for all patients and by main study part (Part A or Part B) in which patients are originally enrolled at the beginning of the study.

In addition, the safety analyses will be performed on the pooled data in the pooled safety analysis set. The summary of safety results will be presented by patient groups defined in Section 2.4.1.

General common rules

All safety analyses will be performed, unless otherwise specified, using the following common rules:

- Safety data in patients who do not belong to the safety analysis set (i.e., exposed but not enrolled) will be listed separately.
- PCSV values are defined as abnormal values considered medically important by the Sponsor according to predefined criteria/thresholds based on literature review and defined by the Sponsor for clinical laboratory tests and vital signs (PCSV version dated January 2009 [[Appendix 10.4](#)]). Considering that the threshold defined in the PCSV list for monocytes and basophils can be below the ULN, the following PCSV criterion will be used for the PCSV analysis of monocytes and basophils:
 - PCSV criterion for monocytes: >0.7 Giga/L or $>ULN$ (if $ULN \geq 0.7$ Giga/L).
 - PCSV criterion for basophils: >0.1 Giga/L or $>ULN$ (if $ULN \geq 0.1$ Giga/L).

- PCSV criteria will determine which patients had at least 1 PCSV during the respective TEAE periods, taking into account all evaluations including unscheduled or repeated evaluations.
- The treatment-emergent PCSV denominator for a given parameter will be based on the number of patients assessed for that given parameter at least once during the respective TEAE periods.
- All measurements, scheduled or unscheduled, fasting or not fasting, will be assigned to Global Analysis Windows defined in [Appendix 10.2](#) in order to provide an assessment for the screening visit through follow-up visit time points.
- For quantitative safety parameters including central laboratory measurements and vital sign scores, descriptive statistics will be used to summarize observed values and change from baseline values by visit.

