5.8.3. Clinical Laboratory Measurements

The following definitions will be applied to laboratory parameters:

- Part A treatment and observation period: the period used for quantitative analysis for Part A is defined from the day after the first study treatment administration to the day of last visit during the Part A observation period.
- Part B treatment period: the treatment period used for quantitative analysis is defined from the day after the first study treatment administration to the day of the last study treatment administration + 28 days for those patients not proceeding into Part C, or up to the day of the first study treatment administration in Part C for those patients proceeding into Part C.
- Part C treatment period: the treatment period used for quantitative analysis is defined from the day after the first study treatment administration in Part C to the day of the last study treatment administration in Part C + 28 days.
- Pooled treatment period: for Part A patients, the treatment period used for quantitative analysis is defined from the day after the first study treatment administration in Part C to the day of the last study treatment administration in Part C + 28 days. For Part B patients, the treatment period used for quantitative analysis is

defined from the day after the first study treatment administration in Part B to the day of the last study treatment administration in Part C + 28 days or to last study treatment administration in Part B + 28 days for patients not entering into the Part C.

For respective treatment period, clinical laboratory parameter actual values (quantitative) and change from baseline values will be descriptively summarized at baseline and each post-baseline visit by at least patient number, mean, median, Q1, Q3, SD, minimum and maximum. Clinical laboratory parameters mean changes from baseline, with the corresponding SE, can be plotted at each visit in the case results warrant further investigation. These parameters will be presented by the biological functions defined in Section 4.8.2. For glucose, only fasting samples will be included in the summaries.

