5.8.5. Analysis of 12-Lead ECG

For respective treatment period as defined for clinical laboratory measurements (Section 5.8.3), ECG parameters will be described through an overall interpretation of ECG status (e.g. normal, abnormal [clinically significant (Yes/No)]).

The count and percentage of patients with at least 1 abnormal post-baseline ECG during the respective TEAE period will be summarized according to the following baseline status categories:

- Normal/missing;
- Abnormal

Individual patient ECG measurements will be additionally evaluated by PCSV criteria, specifically identifying patients with at least one post-baseline measurement that meets the PCSV criteria within the TEAE period. The incidence of PCSVs at any time during the respective TEAE periods will be summarized regardless of the baseline level, and again according to the following baseline categories:

- Normal (according to PCSV criterion/criteria)/missing
- Abnormal according to PCSV criterion or criteria
- Patient listings of ECG measurements that meet PCSV criteria will be provided for the report appendix.
- administration in Part B for patients not entering into the Part C + 28 days.

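### For patients who start Part C on the day of visit 11, the TEAE cut-off moves that visit's pre-dose findings out of the Part A or Part B abnormality counts and into Part C

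*SAP*

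**What the plan says.** **Period boundaries.** SAP 4.8.1 closes the Part A or Part B period one day early for roll-overs: "For patients entering Part C, the TEAE period is truncated at the day before the first study treatment administration in Part C". It then states: "The Part C TEAE period is defined from the day of the first study treatment administration in Part C". Neither rule separates the hours before the dose from those after it. Protocol 11.4.5.1 has the same truncation.

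**What is counted by TEAE period.** SAP 5.8: "PCSV criteria will determine which patients had at least 1 PCSV during the respective TEAE periods". The PCSV denominator is patients assessed at least once in that period. SAP 5.8.3 applies the period to laboratory PCSVs, the peak ALT and bilirubin plot and the sex-hormone combinations, 5.8.4 to vital-sign PCSVs, and 5.9 to the HbA1c PCSV. Appendix 10.3 applies it to the HbA1c criterion for new-onset diabetes. For ECGs, 5.8.5 refers to: "The count and percentage of patients with at least 1 abnormal post-baseline ECG during the respective TEAE period".

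**What is summarised by visit.** SAP 5.8.3 defines a separate treatment period for quantitative summaries. For Part B patients who roll over it runs "up to the day of the first study treatment administration in Part C for those patients proceeding into Part C". For Part A it runs to the last observation-period visit. The Part C equivalent opens the day after the first Part C dose.

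**Roll-over timing.** The footnotes to the protocol's Part C schedule (9.1.1.3) say: "Part C visit 1 should occur on the same day as Part A visit 11 or Part B visit 11", and "Patient can only receive the dose once all assessments from Part A or Part B Visit 11 are completed". SAP 2.3 is more permissive: "The first visit (visit 1) in Part C can occur on the same day as the EOT visit in Part A". Protocol 6.1 is permissive in the same way.

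**Baseline and pooling.** SAP 6.1 takes baseline from before the first dose of the whole study. SAP 2.4.1 keeps Part A data out of the pool, but 4.8.1 sets the pooled TEAE period of Part A patients equal to their Part C TEAE period.

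**The concern.** On a same-day roll-over, visit 11 (week 16 in Part A, week 24 in Part B) is the end-of-treatment visit of the earlier part, and it is completed before any Part C drug is given. The TEAE boundary nevertheless places it in Part C. Because baseline precedes the first dose of the study, the visit 11 value counts as post-baseline in Part C, and an abnormality found then would read as first arising in Part C.

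The SAP also files one measurement in two places. A week 24 laboratory value belongs to Part B in the by-visit table and to Part C in the PCSV table. For Part A patients, a visit 11 value also enters the pooled abnormality counts, despite the rule that Part A data stay out.

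Part B is the phase 3 safety dataset, and the second-step analysis may be used in a submission. ECG and sex hormones are affected most, because visit 11 holds their only scheduled post-baseline assessment before roll-over.

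**Working it through.** The plan states no figure on this point, so there is none to reproduce. The check places the scheduled assessments into the SAP's periods.

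**Inputs.**
- Visit 11 is day 113 in Part A and day 169 in Part B (protocol Tables 1 and 2).
- The last dose is day 1 in Part A and day 141 (week 20) in Part B.
- A same-day roll-over makes the first Part C dosing day 113 or 169.
- Post-baseline assessments through visit 11, in study days:
  - ECG and sex hormones: A 113; B 169.
  - HbA1c: A 113; B 85 and 169.
  - Chemistry and haematology: A 8, 29, 57, 85, 113; B 57, 85, 113, 169.

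**Formula.** End of TEAE period = the smaller of (last dose + 168) and (first Part C dosing day − 1).
- Part A: the smaller of 1 + 168 = 169 and 113 − 1 = 112, so day 112.
- Part B: the smaller of 141 + 168 = 309 and 169 − 1 = 168, so day 168.

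**Result, per same-day roll-over.**

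| Assessment | Part A: in TEAE period | Part B: in TEAE period | Moved to Part C, each part | In by-visit period (A; B) |
|---|---|---|---|---|
| ECG | 0 of 1 | 0 of 1 | 1 | 1 of 1; 1 of 1 |
| Sex hormones | 0 of 1 | 0 of 1 | 1 | 1 of 1; 1 of 1 |
| HbA1c | 0 of 1 | 1 of 2 | 1 | 1 of 1; 2 of 2 |
| Chemistry, haematology | 4 of 5 | 3 of 4 | 1 | 5 of 5; 4 of 4 |

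Vital signs are taken at every visit from 3 to 11, that is at 9 visits after day 1 in each part, and 8 of those 9 remain.

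**Effect on new-onset diabetes.** Suppose a Part B patient has HbA1c below 6.5% at week 12, at or above it at week 24, and below it at all later Part C visits. If week 24 belonged to Part B, it would be the last Part B value and would meet the criterion in Appendix 10.3. Under the written boundary, Part B holds only the normal week 12 value. In Part C the raised value is neither the last nor one of two. The HbA1c criterion is then met in neither part.

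**Analysis windows.** Appendix 10.2 does not settle the matter. Table 2 labels days 155 to 196 as Part B week 24, while Table 4 labels Part C day 1 as week 0. PCSVs are in any case counted at any time in the TEAE period, whatever the visit label.

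**After the fix.** With pre-dose assessments assigned to the preceding part, the counts become 1 of 1 for ECG and sex hormones in both parts, 1 of 1 and 2 of 2 for HbA1c, and 5 of 5 and 4 of 4 for chemistry and haematology.

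**The case against.** Several limits stand.

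- **Visit 11 is not lost.** By-visit means, the overall ECG interpretation in 5.8.5, sex-hormone values by time point and HbA1c by visit all use the treatment period and keep it in Part A or B. The pooled TEAE period of Part B patients is continuous and captures it. PCSV listings are also provided. Only the counts of patients with any abnormality are affected.
- **The study is single-arm and its safety summaries are descriptive.** No between-group comparison is biased.
- **Same-day roll-over is not guaranteed.** One footnote says it should happen; protocol 6.1 and SAP 2.3 say only that it can. Protocol 11.4.3.3 foresees a prolonged gap before Part C for some patients.
- **The 5.8.3 boundary is not a clean model.** It works by whole days. Vital signs are also taken 30 and 60 minutes after each infusion, so copying it would put readings taken after the first Part C infusion into Part B. For Part A it contains no Part C dosing boundary to copy.

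Two stronger readings are tempting. A reader might infer that the ECG and hormone abnormality tables will be empty, at 0 of 14 in Part B and 0 of 6 in Part A. That needs every planned patient to roll over on the same day with no unscheduled test; if half do so, 7 of 14 and 3 of 6 remain. Protocol 3.2.1 assumes that all patients enter Part C, but only to compute study duration, and it says nothing about same-day entry. A denominator rule is also stated only for PCSVs, not for the abnormal-ECG or hormone-combination counts.

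A reader might also infer that the SAP alone is at fault. It is not. Protocol 11.4.5.1 has the same truncation, and protocol 11.4.5.2 is mixed: its definition uses the TEAE period and its analysis text uses the treatment period.

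**Conclusion.** The point holds for same-day roll-overs and for assessment-based counts of any abnormality. For these patients the written boundary files pre-dose visit 11 findings under Part C, while the by-visit summaries keep the same values in Part A or B. It removes the only scheduled post-baseline ECG and sex-hormone sample from both parts and the only HbA1c from Part A. Elsewhere it removes one value among several. It also lets Part A visit 11 values into the pooled counts of Part A patients.

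The counts assume nominal visit days, visit 11 on the first Part C dosing day, and no unscheduled tests. How many patients this covers cannot be known from the documents. The primary endpoint, the adverse-event onset rule, the by-visit summaries and the pooled counts of Part B patients are unaffected. This is a misattribution between study parts that should be fixed; it does not undermine the study's main conclusions.

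**What to change.** In SAP 5.8, 5.8.3, 5.8.4, 5.8.5, 5.9 and Appendix 10.3, add one rule for assessment-based safety counts on the day of the first Part C dose:

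- Assessments taken before that dose belong to the preceding part (A or B). They are excluded from the Part C counts and from the pooled counts of Part A patients.
- Assessments taken after that dose, such as the 30- and 60-minute vital signs, belong to Part C.

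Use this time-based split rather than the day-level boundary of 5.8.3. Reconcile the two statements in protocol 11.4.5.2 so that the PCSV definition and the PCSV analysis name the same period. Leave the adverse-event onset rule in SAP 4.8.1 and protocol 11.4.5.1 as it is.

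The cost is a wording change in the SAP, a clarification in the protocol and one derivation rule in the programs. No new data are needed: SAP 6.3 says the time of each administration is entered in the e-CRF, and the protocol already requires all visit 11 assessments to precede the dose.
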